7.2. Key Secondary Efficacy Analysis

The key secondary endpoint is the proportion of subjects achieving success on the IGA of the Assessment Area, where success on the IGA is defined as at least a 2-point reduction from Baseline to Visit 6 (Week 8). Subjects whose status at Visit 6 is unknown will be defined as non-responders. The key secondary endpoint will be analyzed using the CMH test, as described for the primary analysis. However, if the primary analysis is not statistically significant, then the results for the key secondary endpoint will be exploratory rather than confirmatory. This fixed sequence testing procedure maintains the overall level of significance for the primary and key secondary endpoints.

7.3. Other Secondary Efficacy Analyses

All other secondary endpoints will be analyzed using two-sided tests at the $\alpha=0.05$ level of significance, with no adjustment for multiplicity.

7.3.1. Percent Change in Reference Lesion Surface Area (LSA)

Descriptive statistics of the percent change in Reference Lesion surface area from Baseline to Visit 6 (Week 8) will be presented by treatment. An Analysis of Covariance (ANCOVA) model with treatment, genotype, and age group as fixed effects and baseline surface area of the Reference Lesion as a covariate will be used to analyze the data. Treatment differences in the percent change from baseline between Diacerein 1% Ointment and Control Ointment will be evaluated by the least-squares mean, standard error, 2-tailed 95% confidence interval, and a 2-sided p-value.

7.3.2. BSA success at Visit 8 (Week 16)

The proportion of subjects who achieve $\geq 60\%$ reduction in BSA of EBS lesions from Baseline to Visit 8 (Week 16) will be analyzed using the CMH test, as described for the primary efficacy endpoint.

7.3.3. IGA Success at Visit 8 (Week 16)

The proportion of subjects achieving success on the IGA of the Assessment Area, where success on the IGA is defined as at least a 2-point reduction from Baseline to Visit 8 (Week 16), will be analyzed using the CMH test, as described for the primary efficacy endpoint.

7.4. Exploratory Efficacy Analyses

Descriptive statistics for the exploratory endpoints will be presented by treatment group at each visit. All exploratory efficacy analyses will be conducted using two-sided tests at the $\alpha=0.05$ level of significance, with no adjustment for multiplicity.

7.4.1. Reduction in Pain Intensity at Visit 6 (Week 8) and Visit 8 (Week 16)

The proportion of subjects with a reduction in overall pain intensity from Baseline to Visit 6 (Week 8) and Baseline to Visit 8 (Week 16) will be analyzed in the same manner as described previously for the IGA success at Visit 6 (Week 8). The overall pain intensity at a given visit will be based on the average of the subject's reported pain intensity from the 7 days prior to the visit assessment, based on the data collected from the subject's eDiary.

7.4.2. Reduction in Pruritus Intensity at Visit 6 (Week 8) and Visit 8 (Week 16)

The proportion of subjects with a reduction in overall pruritus intensity from Baseline to Visit 6 (Week 8) and Baseline to Visit 8 (Week 16) will be analyzed in the same manner as described previously for the IGA success at Visit 6 (Week 8). The overall pruritus intensity at a given visit will be based on the average of the subject's reported pruritus intensity from the 7 days prior to the visit assessment, based on the data collected from the subject's eDiary.

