7.3. Inclusion Criteria

In order to be eligible for the study, subjects must fulfill all of the following criteria:

1. Subject is male or female at least 4 years of age at Visit 1
2. Subject has a documented genetic mutation consistent with EBS. A blood or saliva sample will be collected for genetic confirmation if no documented gene mutation data is available. Gene mutations acceptable for inclusion are as follows: KRT5, KRT14, PLEC1, TGM5, PKP1, DSP, FERMT1, EXPH5, DST, KLHL24.
3. Subject has an Assessment Area (see Section 9.1.2) of EBS lesions to be treated, that is $\geq 2\%$ body surface area (BSA) and the EBS lesions are in one or both of the following body areas:

- Localized: plantar and/or palmar areas (plantar areas where >25% of the area has hyperkeratosis that has been present for greater than 12 weeks cannot be included as part of the Assessment Area
 - Generalized: arms, legs, torso, hands and feet (scalp, groin and areas where, in the investigator's opinion, the study medication might become occluded cannot be included as part of the Assessment Area)
4. Subject's EBS lesions in the Assessment Area have an Investigator's Global Assessment (IGA) score of ≥ 3
 5. Subject/caregiver agrees to not use any topical therapies other than the study medication that might influence the status of the EBS lesions during the duration of the study (*e.g.*, medicated cleansers, CBD oil, MediHoney, Silvadine cream 1%, [see Section 7.5.3]; the Investigator should consult the Medical Monitor regarding therapies not specified in the protocol
 6. Subject/caregiver agrees to follow topical product application instructions (see Section 7.5.4) during the treatment period
 7. If the subject is a woman of childbearing potential, she has a negative urine pregnancy test and agrees to use an approved effective method of birth control, as defined by this protocol (see Section 10.6), for the duration of the study.
 8. Subject is non-pregnant, non-lactating and is not planning for pregnancy during the study period
 9. Subject is in good general health and free of any known disease state or physical condition which, in the investigator's opinion, might impair evaluation of the EBS lesions or which exposes the subject to an unacceptable risk by study participation
 10. Subject is willing and able to follow all study instructions and to attend all study visits
 11. Subject/caregiver is able to comprehend and willing to sign an Informed Consent and/or Assent Form.

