9.1.6. Pruritus Intensity (for Subjects aged 8 years and older)

The Pruritus Intensity Assessment is the subject's assessment of **pruritus at its worst** experienced **over the previous 24 hours** on all EBS lesions. *The subject should NOT refer to any other assessments to assist with these assessments.*

Starting at Visit 2 (Week 0) and **continuing each day** for the duration of the subject's study participation, the subject will report his/her experience of pruritus at its worst in an **electronic diary**.

This assessment should be completed just prior to the daily study medication application using the following scale:

Pruritus Intensity											
Instructions: The following question is about itch related to your epidermolysis bullosa simplex (EBS). Please select the number that best describes your experience with itch at its worst over the past 24 hours . Please select only one answer. There is no right or wrong answer to this question.											
Rate your itch at its worst over the past 24 hours.	0	1	2	3	4	5	6	7	8	9	10
											
	No itch at all										Worst possible itch

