9.1.7. Pain Intensity (for Subjects aged 8 years and older)

The Pain Intensity Assessment is the subject's assessment of **pain at its worst** experienced **over the previous 24 hours** on all EBS lesions. The subject should NOT refer to any other assessments to assist with these assessments.

Starting at Visit 2 (Week 0) and continuing each day for the duration of the subject's study participation, the subject will report the average overall intensity of pain in an electronic diary.

This assessment should be completed just prior to the daily study medication application.

Pain Intensity											
Instructions: The following question is about pain related to your epidermolysis bullosa simplex (EBS). Please select the number that best describes your experience with pain at its worst over the past 24 hours . Please select only one answer for each question. There is no right or wrong answer to this question.											
Rate your pain at its worst over the past 24 hours.	0	1	2	3	4	5	6	7	8	9	10
											
	No pain at all										Worst possible pain

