9.1.8. Mobility Assessment

The Mobility Assessment is the subject/caregiver's assessment of the subject's degree of mobility over the previous 24 hours. The subject/caregiver should NOT refer to any other assessments to assist with these assessments. The same individual, subject or caregiver, should perform all Mobility Assessments for a given subject for the duration of the study. Note that the assessment of pain and pruritus must be done by the subject.

Starting at Visit 2 (Week 0) and continuing each day for the duration of the subject's study participation, the subject/caregiver will report the subject's degree of mobility by answering a series of age-appropriate questions in the eDiary. This assessment should be completed at approximately the same time each day, just prior to the study medication application, using the following scale:

Score	Definition
1	Uses wheelchair (May stand for transfers, may do some stepping supported by another person or using a walker/ frame)
2	Uses walker or frame: Without help from another person
3	Uses crutches: without help from another person
4	Uses sticks (e.g. , canes) (one or two): Without help from another person
5	Independent on level surfaces: Does not use walking aids or need help from another person (if uses furniture, walls, fences, shop fronts for support use 4 description). Requires rails for stairs
6	Independent on all surfaces: Does not use any walking aids or need any help from another person when walking over all surfaces including uneven ground, curbs, etc. and in a crowded environment
7	Crawling: Child crawls for mobility at home
8	Does not apply: For example, child does not complete the distance

This scale is assessed for 3 distances: 5 meters (yards); 50 meters (yards); 500 meters (yards).

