4. ANALYSIS POPULATIONS

4.1. Intent-to-Treat Population

The Intent-to-Treat (ITT) Population will consist of all randomized subjects who are dispensed study medication. All efficacy analyses will be conducted using the ITT population. Subjects will be included in the treatment group to which they were randomized.

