For the key secondary endpoint, the same imputation methods will be employed as with the primary endpoint. No imputation will be performed on the other secondary or exploratory endpoints.

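### The exploratory pain and pruritus analyses lack a defined denominator: children under 8 are never asked, the SAP's rules for a missing score conflict, and zero-baseline subjects cannot respond

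*SAP*

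**What the plan says.** - **Who is asked.** Protocol 9.1.6 and 9.1.7 carry the age limit in their headings: "Pruritus Intensity (for Subjects aged 8 years and older" and "Pain Intensity (for Subjects aged 8 years and older". Protocol 9.1.8 excludes proxy reports: "Note that the assessment of pain and pruritus must be done by the subject".
- **Who is enrolled.** Protocol 7.3: "Subject is male or female at least 4 years of age at Visit 1". Randomisation has a stratum for age under 8, so children aged 4 to 7 are expected.
- **Who is analysed.** SAP 4.1: "All efficacy analyses will be conducted using the ITT population". The ITT set is everyone randomised and dispensed medication. Age 8 appears in the SAP as a stratification and imputation variable, never as a limit on the pain or pruritus endpoints.
- **How.** SAP 7.4.1 and 7.4.2 say that these endpoints "will be analyzed in the same manner as described previously for the IGA success at Visit 6 (Week 8". In that analysis, SAP 7.2: "Subjects whose status at Visit 6 is unknown will be defined as non-responders".
- **The competing rule.** SAP 5.5: "No imputation will be performed on the other secondary or exploratory endpoints". SAP 3.1.4 lists all four pain and pruritus endpoints as exploratory.
- **Response and baseline.** Response is any reduction (SAP 3.1.4). Baseline is the single diary value from the first treatment day (SAP 6.3), and follow-up is a 7-day average (SAP 7.4). No minimum pain or pruritus score is required at entry.

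**The concern.** Two groups cannot be responders, whatever the treatment does.

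Children under 8 have no score because the design never asks for one. Nothing in the SAP separates a score that was never sought from one that went missing. Two programmers could follow SAP 7.2 and SAP 5.5 respectively and print different denominators and percentages from the same data.

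Subjects aged 8 or older with a baseline of 0 do have a score, but it cannot fall. The borrowed IGA method does not have this difficulty: entry requires an IGA of at least 3, so a 2-point drop is always possible. Because baseline is one day's value, a single symptom-free day fixes a subject as a non-responder.

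At stake are the reported proportions, which are how these endpoints are defined, and the precision of the comparison.

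**Working it through.** **The plan's own figure.** None is given for pain or pruritus. The only power statement (SAP 11) is for BSA: 80 subjects, 60% versus 30%, two-sided alpha 0.049, 77% power. With 40 per arm and pooled variance under the null, power = Φ[(|p1 − p2|√n − z√(2p̄q̄)) / √(p1q1 + p2q2)] = Φ[(1.897 − 1.385)/0.671] = 77.7%, so it reproduces.

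**Assumptions.** The documents do not give the share under 8, the share with zero baseline, or response rates for these symptoms. All are assumed below.

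**1. Children under 8, if SAP 7.2 governs.** With share f under 8 and true rate p in the others, the printed proportion is p(1 − f).

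| f | 60% prints as | 40% prints as |
|---|---|---|
| 10% | 54% | 36% |
| 20% | 48% | 32% |
| 30% | 42% | 28% |
| 40% | 36% | 24% |

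If SAP 5.5 governs and children without a score are left out, the printed figures stay at 60% and 40%.

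**2. Effect on the stratified test.** In a stratum with no responders, the CMH numerator term (a − n1·m/N, with m = 0) is 0, its variance term is 0, and it adds 0 to both parts of the Mantel-Haenszel relative risk. Numerical check, stratifying on age only: 32 per arm aged 8 or older with 19 and 10 responders, plus 8 per arm under 8 entered as failures. The crude ITT proportions are 19/40 = 47.5% and 10/40 = 25.0%, against 59.4% and 31.3% at age 8 or older. The CMH chi-square is 5.03, p = 0.0249 and relative risk 1.90, with or without the under-8 stratum. The same argument covers each genotype-by-age stratum under 8.

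**3. Zero baseline, under either rule.** Baseline score is not a stratum, so these subjects do not drop out. Take 30 per arm aged 8 or older, true 60% versus 40% among those able to improve, and share g at zero in both arms. Unpooled z = difference / √[(p1q1 + p2q2)/n].

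| g | Counted: rates, n = 30 | z | Excluded: n at 60/40 | z | Ratio of z² |
|---|---|---|---|---|---|
| 10% | 54/36 | 1.42 | 27 | 1.50 | 1.11 |
| 20% | 48/32 | 1.28 | 24 | 1.41 | 1.22 |
| 30% | 42/28 | 1.15 | 21 | 1.32 | 1.325 |

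For g = 10%: 0.18/√(0.4788/30) = 1.42, against 0.20/√(0.48/27) = 1.50. The expected relative risk stays at 1.5 (0.54/0.36), so with balanced zeros the loss is in the risk difference and in precision.

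**4. Larger assumed effect.** Borrowing the BSA rates (60% versus 30%), with 32 per arm aged 8 or older and two-sided alpha 0.05, power with zeros counted versus excluded is 64.0% versus 65.9% (5% at zero), 59.9% versus 63.5% (10%), 51.6% versus 58.2% (20%) and 43.8% versus 52.4% (30%). The loss is about 2 to 9 points.

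**The case against.** A reader might infer that every child under 8 is scored as a failure by design. The documents do not support that. SAP 5.5 bars imputation for exploratory endpoints, SAP 3.1.4 puts pain and pruritus in that class, and SAP 12 records the Week 8 versions as moved there deliberately. The phrase about analysing in the same manner can mean the stratified CMH test alone. On that reading, unasked children fall out as missing. This objection stands against the stronger inference, but it leaves a conflict between two SAP sections and no stated denominator.

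A reader might also infer a threat to the trial's conclusions, because pain and pruritus are the only efficacy items among the secondary objectives in SAP 2.1. But SAP 7.4 tests them as exploratory endpoints without multiplicity adjustment, and the SAP claims no power for them.

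On zero baselines, counting an observed non-reduction in the full ITT set is a legitimate choice of target population. Zeros may also be uncommon: entry requires an IGA of at least 3, the diary asks for the worst score over 24 hours, and the protocol's introduction describes pain and severe itch. In step 3 the loss in z is only 0.08 to 0.17, and no value reaches 1.96 either way. All of this limits the size of the point. It does not change the fact that a score of 0 cannot fall, or that the plan leaves the choice unstated.

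**Conclusion.** The point holds as a minor one. The denominator for pain and pruritus is undefined, and SAP 7.2 (reached through 7.4) conflicts with SAP 5.5 on subjects without a score. Only if SAP 7.2 governs do children under 8 lower the printed proportions, in relative terms by their share of the sample. The stratified p-value and relative risk are unaffected even then. Zero-baseline subjects weaken the comparison under both rules: in the illustrations, excluding them is worth about 11% to 33% more subjects for 10% to 30% at zero. These sizes rest on assumed shares, assumed response rates and an assumed 30 or 32 per arm aged 8 or older. Primary and key secondary inference is untouched.

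**What to change.** In SAP 3.1.4 and 7.4:

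- Define the analysis set separately for each symptom as ITT subjects aged 8 or older at randomisation with a baseline score above 0 for that symptom. Use it as the denominator in tables and tests.
- State whether the non-responder rule of SAP 7.2 or the no-imputation rule of SAP 5.5 applies to a missing visit score within that set. Restricting the set by age and baseline does not settle this.
- Report, by arm, how many subjects were not assessable because of age and how many because of a zero baseline.

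The cost is a few SAP sentences and a table footnote, and SAP 1 allows revisions before database lock. Both restrictions rest on baseline facts, since Protocol 9.1.6 and 9.1.7 place the diary score just before application, so they should not bias the comparison. The small downside is that the result then describes symptomatic subjects aged 8 or older, not the whole ITT set. A full-ITT version can be shown alongside.

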8. ANALYSIS OF SAFETY

Safety will be assessed using the Safety Population. The assessment of safety will include adverse events, clinical laboratory assessments, ECGs, physical examinations, and vital signs. The safety analysis will be based primarily on the frequency of new or worsening adverse events, laboratory abnormalities, and serious adverse events (SAEs). Other safety data will be summarized as appropriate.

8.1. Extent of Exposure

Amount of study drug used will be summarized by treatment group for the Safety Population using descriptive statistics. Study drug usage is based on data collected from the Drug Accountability eCRF where drug usage is calculated as the amount of study drug dispensed minus the amount of study drug returned, in grams.

Percent compliance with the study medication will be summarized by treatment group for the Safety Population using descriptive statistics. Compliance with study medication application is based on data collected from the subject's eDiary. The analysis will include listings for drug exposure and compliance.

8.2. Adverse Events

Adverse events will be coded using the Medical Dictionary for Regulatory Activities (MedDRA) version 19.0 and summarized by treatment group, system organ class, and preferred term.

A summary overview of TEAEs will be provided which presents the number and percentage of patients in each treatment group satisfying each of the following categories:

- All TEAEs,
- Drug-related TEAEs,
- Maximum severity of TEAEs,
- Maximum severity of drug-related TEAEs,
- All AESIs,
- Drug-related AESIs,
- Maximum severity of AESIs,
- All treatment-emergent SAEs,
- Drug-related treatment-emergent SAEs,
- Death due to TEAEs,
- TEAEs leading to study drug discontinuation, and
- Drug-related TEAEs leading to study drug discontinuation.

The numbers and percentages of patients with TEAEs will be summarized by MedDRA preferred term within system organ class, by treatment group and overall. For the summaries by treatment group, multiple AEs with the same MedDRA preferred term within system organ class from the same patient within a given treatment will only be counted once. For overall summaries, multiple AEs with the same MedDRA preferred term within system organ class from the same patient will only be counted once.

All TEAEs related to study drug, AESIs, SAEs, and AEs leading to study drug discontinuation will be summarized in the same manner. Summaries will also be provided for the numbers and

percentages of patients by system organ class, preferred term, and maximum severity, for TEAEs, AESIs, and drug-related TEAEs.

All AEs will be included in by-patient listings containing additional information of interest such as onset and resolution times, maximum severity, causal relationship to study medication, and action taken. Specific by-patient listings of AESI, SAEs, and TEAEs leading to study discontinuation will be provided.

8.3. Safety Laboratory Parameters

Clinical laboratory results will be summarized with descriptive statistics by treatment and visit. Change from baseline will also be summarized. Laboratory values will also be listed by visit, within patient.

8.4. Vital Signs

Vital signs and the change from baseline will be summarized descriptively by treatment and visit. The count and percentage of subjects with abnormal values will be summarized by treatment and visit. Abnormal blood pressure measurements for subjects age 17 and younger will be defined as either systolic or diastolic measurements above the 95th percentile, according to height, sex, and age. Abnormal blood pressure measurements for subjects age 18 and older will consist of either a systolic blood pressure >140mm Hg or a diastolic blood pressure >90mm Hg. Abnormal weight measurements for subjects age 18 and older will be defined as measurements > 300 pounds (>118 kilograms). Abnormal BMI measurements for subjects age 17 and younger will be defined as measurements above the 95th percentile, according to sex and age. Abnormal values will be defined as clinically relevant (CR) or not clinically relevant (NCR) on the eCRFs. Vital sign data will also be listed by visit, within patient.

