3.2. Safety Variables

3.2.1. Adverse Events

Adverse events (AEs), which include clinical laboratory test variables, will be monitored and documented from the time of the first study medication application until the subject's study participation is complete (Week 16). Beginning with the start of the first study medication

application, investigators should make an assessment for adverse events at each visit and record the event on the appropriate AE electronic Case Report Form (eCRF). All AEs that occur after the first study medication application and up to 30 days after the subject's last study medication application will be considered treatment-emergent adverse events (TEAEs).

In concert with system-organ classification (SOC) defined by MedDRA the following AEs will be categorized as AEs of special interest (AESIs) in this study:

- All gastrointestinal (GI) disorders defined by MedDRA SOC
- Hepatic Injury
- Pancreatitis
- Urticaria/angioedema
- Epidermal necrolysis
- Drug reaction with eosinophilia and systemic symptoms (DRESS)
- Purpura/cutaneous vasculitis
- Jaundice

Each AE shall be evaluated for the severity, seriousness, duration, resolution, action taken and its relationship with the study medication.

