6.3. Demographics and Baseline Characteristics

Demographic and baseline characteristics will be summarized by treatment for each of the analysis populations. Demographic and baseline characteristics include the following: age at informed consent, sex, race, ethnicity, genotype, IGA score at baseline, BSA of assessment area at baseline BSA of treatment area at baseline, total BSA of all EBS lesions at baseline, pruritus severity at baseline, pain severity at baseline, and mobility score at baseline. Unless otherwise stated, all continuous variables will be represented by n, mean, standard deviation, minimum, median, and maximum. All categorical variables will be presented as counts and percentages. Demographic characteristics will also be listed.

Baseline for all analysis variables will be the last measurement prior to the first application study medication, unless otherwise stated. For data collected from the eDiary, Baseline will be the value recorded from the first day that the subject received study medication.

Medical history will be summarized for the number and percentage of patients for each medical term. Medical history information will be listed. A listing of concomitant therapies/procedures will be provided.

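### SAP 8.4 sets only upper limits for abnormal blood pressure, adult weight and child BMI, so its by-arm abnormal count cannot show low values, weight loss or new onset

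*SAP*

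**What the plan says.** SAP 8.4 opens with "Vital signs and the change from baseline will be summarized descriptively by treatment and visit", and then states: "The count and percentage of subjects with abnormal values will be summarized by treatment and visit". It gives four numeric definitions of abnormal:

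- Blood pressure, age 17 and younger: systolic or diastolic over the 95th percentile for height, sex and age.
- Blood pressure, age 18 and older: "systolic blood pressure >140mm Hg or a diastolic blood pressure >90mm Hg".
- Weight, age 18 and older: over 300 pounds, also given as 118 kg.
- BMI, age 17 and younger: "Abnormal BMI measurements for subjects age 17 and younger will be defined as measurements above the 95th percentile, according to sex and age".

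The section gives no limits for pulse, temperature, respiration, child weight or adult BMI. It also plans a by-visit listing for each patient and refers to the rating of abnormal values as clinically relevant or not on the eCRF, which Protocol 9.2.2 requires as well.

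SAP 6.3 sets the baseline rule, "Baseline for all analysis variables will be the last measurement prior to the first application study medication", and describes continuous variables by "n, mean, standard deviation, minimum, median, and maximum". Weight is measured at Visits 1, 6 and 8 (Protocol 9.2.2, SAP 3.2.3).

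Protocol 10.1 has clinically significant examination findings reported as adverse events. SAP 8.2 then provides: "The numbers and percentages of patients with TEAEs will be summarized by MedDRA preferred term within system organ class". Under SAP 3.2.1, events after the first application and up to 30 days after the subject's "last study medication application will be considered treatment-emergent adverse events". The same section makes all gastrointestinal disorders events of special interest.

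**The concern.** A table of abnormal counts by arm is where a reader looks for how many subjects moved to a worrying value. Here its stated limits point in one direction only.

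Protocol 8.8.8 records moderate to severe diarrhea with oral diacerein, and Table 2 in SAP 12 shows that the special-interest list was widened to all gastrointestinal disorders. As a matter of clinical inference, fluid loss would lower weight and blood pressure. The stated limits look for the opposite. Subjects may be as young as 4 (Protocol 7.3).

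High weight and high child BMI are also likely to be present at entry. With no baseline condition and no shift table, a subject who was already above the limit is counted in the same way as one who newly crossed it.

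The stake is how readable one safety table is. Efficacy, alpha, sample size, dosing rules and adverse event detection are not affected.

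**Working it through.** **1. The one figure in the section that can be checked.** 300 lb × 0.45359237 = 136.1 kg, and 118 kg / 0.45359237 = 260.1 lb, so the two adult weight limits disagree. That is a separate error. Either way the limit is an upper one.

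**2. Direction of the limits.** Of the four definitions, 4 are upper limits, 0 have a lower limit and 0 refer to baseline.

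**3. The limits applied to illustrative values (assumed).**

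| Case | Test | Counted as abnormal? |
|---|---|---|
| Adult, 80/45 mm Hg | 80 > 140 no; 45 > 90 no | No |
| Adult, 70 to 60 kg (−10/70 = −14.3%) | 60 > 118 no | No |
| Adult, 125 to 112 kg (−13/125 = −10.4%), 118 kg limit | 125 > 118 yes; 112 > 118 no | Yes at entry, no after the loss |
| Child, 20 to 18 kg (−2/20 = −10%) | no child weight limit; BMI limit is upper only | Not for the loss |

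**4. What the other displays give.** Mean change shows an average shift. If the SAP 6.3 statistics apply to 8.4, the minimum change shows the largest single fall in each arm. Listings show every value. None of these gives the number of subjects per arm who fell by a relevant amount.

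**5. New versus present at entry.** By definition 5% of reference children exceed the 95th BMI percentile. With an assumed 20 children per arm (half of the 80/2 = 40 planned), that is 0.05 × 20 = 1.0 child per weight visit. Under a bivariate normal model with an assumed baseline-to-follow-up correlation r:

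- r = 0.90: P(above at both visits) = 0.0319. Share already above at entry: 0.0319/0.05 = 64%. New: (0.05 − 0.0319) × 20 = 0.36.
- r = 0.97: P(above at both visits) = 0.0400. Share already above at entry: 80%. New: (0.05 − 0.0400) × 20 = 0.20.

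Most high-BMI flags would therefore describe entry status.

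**6. Chance flags from possible additions.**

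- Child BMI below the 5th percentile: by symmetry with step 5, 1.0 per 20 per visit, of which 0.20 to 0.36 are new since baseline.
- Adult systolic below 90, assumed mean 120: SD 12 gives z = −2.5, P = 0.0062, × 20 = 0.12; SD 15 gives z = −2, P = 0.0228, × 20 = 0.46.
- Weight loss of at least 5%, assumed mean change 0, arm of 40: SD 2, 3 and 4 give P = 0.0062, 0.0478 and 0.1056, so 0.25, 1.91 and 4.23 subjects.
- Weight loss of at least 10%: SD 4 gives z = −2.5, P = 0.0062, × 40 = 0.25; smaller SDs give fewer.
- Child systolic or diastolic below the 5th percentile: a simulation of 400,000, with assumed systolic/diastolic correlation 0.3 to 0.7 and visit-to-visit correlation 0.5 to 0.7, gives 3 to 5 of 20 children with at least one new flag over Visits 3 to 8.

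**7. Weight interval.** There is no Visit 2 weight, so the baseline is Visit 1, up to 42 days before randomization. To Visit 6: 42 + 56 = 98 days at most, 56/98 = 57% on treatment. To Visit 8: 42 + 112 = 154 days, 56/154 = 36% on treatment. Both are before the ±4-day visit windows.

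**The case against.** The best reply is that this is preference rather than error. A screen for high values, with change-from-baseline summaries and full listings, is an ordinary Phase 2 descriptive display, and SAP 8.4 contradicts nothing else in the plan. Diarrhea, the most plausible route to weight loss, is covered more directly: all gastrointestinal disorders are events of special interest and are counted by arm with maximum severity, and moderate or severe diarrhea stops treatment. Neither special-interest list names hypotension or weight loss, and Protocol 3 reports serum rhein below 1% of the oral level in two patients. All of this stands and keeps the point small. It does not supply the missing count.

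Three stronger readings are tempting, and the documents support none of them.

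- **The whole abnormal table shows highs only.** Pulse, temperature and respiration have no numeric limit in SAP 8.4. If they enter the count, it must rest on something else, possibly the eCRF rating, for which no direction is stated. The same silence means one cannot claim that investigators' ratings certainly capture low values.
- **Low values are lost, or nothing is compared with baseline.** Change from baseline is in the opening sentence of the section. Because the count is by visit, an entry count per arm may also be available beside the later ones. Only within-subject transitions are missing.
- **Late falls escape the adverse event tables.** The 30-day window covers Visit 6 but not Visit 8. However, SAP 8.2 also speaks of summarising adverse events without that limit, Protocol 11.2.4 summarises new or worsening events after dosing with no 30-day cap, and all events are listed.

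**Conclusion.** The point holds for blood pressure, adult weight and child BMI. All four stated limits are upper limits and no categorical shift table is planned. The by-arm count for these parameters therefore cannot register low blood pressure, low child BMI or weight loss, and cannot separate new abnormalities from those present at entry. The gap is the per-arm number of subjects with a low value or a marked fall.

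The direction of the limits comes from the text and needs no assumption. The sizes in the working do: the child/adult split, correlations, means and SDs are assumed because the documents give none, and reference percentiles need not describe children with EBS. Nothing here shows that a safety signal would be hidden. This is a cheap improvement that the sponsor could make.

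**What to change.** In SAP 8.4, keep the existing counts and add, by arm:

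1. The number of subjects losing at least 10% of weight, with at least 5% as supportive, at Visit 6 (main) and Visit 8 (off treatment). Footnote that the weight baseline is Visit 1, so the change to Visit 6 spans up to 98 days, of which 56 are on treatment. The 10% count is the more specific: at most 0.25 chance subjects per arm of 40, against 0.25 to 4.23 for 5%.
2. An adult low blood pressure limit, for example systolic below 90 mm Hg, and a low BMI limit for age 17 and younger, for example below the 5th percentile. The medical monitor should confirm the cut-offs, which are assumed here.
3. A low/normal/high shift display from baseline to post-baseline, beside the counts and not replacing them, so that subjects abnormal at entry stay visible. Where no lower limit is set, it reduces to normal/high.

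Do not add a 5th-percentile low blood pressure flag for children. With 3 to 5 of 20 flagged at least once by chance, it would add mostly noise. Low readings in children stay visible through the change summaries and listings, and through adverse events when clinically significant.

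The cost is SAP wording and a slightly longer table, with no new procedures. A few chance low flags will appear in both arms, so flags should be shown by visit and compared between arms.
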